2. ADEQUACY OF PROTECTION AGAINST RISKS

a. Recruitment and Informed Consent

- Describe plans for the recruitment of subjects (where appropriate) and the process for obtaining informed consent. If the proposed studies will include children, describe the process for meeting requirements for parental permission and child assent.
- Include a description of the circumstances under which consent will be sought and obtained, who will seek it, the nature of the information to be provided to prospective subjects, and the method of documenting consent.

After obtaining approval from the IRB, admitted SLE patients will be referred by their physician for participation in the study, who will provide a letter that will explain the study and provide participants a number to call if they have questions or concerns prior to agreeing to participate. Participants who indicate interest in the study will be immediately screened for eligibility, and if eligibility criteria are met, informed consent will be obtained. Once a patient has been consented, they will be randomized to membership in one of the two study arms. assigned to the intervention (complete questionnaires and phone sessions) or control (complete questionnaires only) arm, and the rest of the recruitment visit will include baseline self-report assessments and scheduling of phone sessions (if applicable).

b. Protection against Risk

- Describe planned procedures for protecting against or minimizing potential risks, including risks to confidentiality, and assess their likely effectiveness.
- Where appropriate, discuss plans for ensuring necessary medical or professional intervention in the event of adverse effects to the subjects.
- Studies that involve clinical trials (biomedical and behavioral intervention studies) must include a description of the plan for data and safety monitoring of the research and adverse event reporting to ensure the safety of subjects in Section 4 below.

Given the complexity of SLE and the overall study goal to provide modeling and reinforcement by a lay patient navigator to lupus patients to encourage them to engage in activities that promote the learning of disease self-

management skills and support their practice of these learned skills, every attempt will be made to ensure that the study/navigation does not negatively impact the patient. To address this potential concern the following approach will be implemented:

1. Upon hiring, lay patient navigators will receive training, prior to working with patients.
2. Lay patient navigators will be given a written manual presenting all the material in detail for their ongoing reference.
3. Lay patient navigators will be given parameters for their roles and instructed on how to handle potential issues that may arise (e.g. not providing clinical advice) along with role-playing.
4. After the initial training, the lay patient navigator will continue to meet with the PI weekly to identify challenges and reinforce the guidelines of the study. During these meetings, the PI will also monitor the lay patient navigator's comfort with interactions with patients. If the lay patient navigator express discomfort and/or feeling overwhelmed, the study will be terminated.
5. Weekly phone calls to patients and PI meetings with the lay patient navigator will be used to track participant satisfaction with the navigation process.

Additional protections against potential risks include the following:

1. Psychological Distress: Because we will be administering a questionnaire that measures the presence of depression, we will take several steps to ensure the safety of research participants. Research personnel will be trained by the PI to identify patients who meet criteria for depression on the PHQ-9. Participants who screen positive for depression will be assessed by a clinician before leaving their study visit to ensure their well-being and verbally instructed to seek care from their PCP. If deemed appropriate, they will also be given the Suicide Prevention National Hotline, [name], and told to call if they experience acute worsening of symptoms before they can be seen by their PCP.
2. Administration of Research Questionnaires: Some participants might be offended by detailed questions about emotional or physical health status and impairment. All participants will be informed at the outset that they may terminate participation at any point. Past research suggests that data collection using these measures can be conducted without undue psychological distress or exacerbation of symptoms among study participants.
3. Unknown risks: Participation in research may have other unknown risks. The researchers will advise participants if they learn of emerging information that might alter participants' decisions to participate.

Participants requiring medical or other professional intervention for study-related events will be provided with appropriate and timely medical guidance by the PI. If adverse events occur during the conduct of this study, they will be reported to the MUSC IRB in accordance with Section 4.7 - Unanticipated Problems and Adverse Events Policy and Procedures.

To protect against the potential risk of loss of confidentiality and/or breach of privacy, data will be compiled using codes in lieu of personal identifiers. Access to study data will be limited to research personnel. Development of and security oversight for the electronic database for this study will be performed by the PI and study statistician. Paper documents pertaining to this study will be stored in locked file cabinets and electronic data will be entered into secure, password-protected databases developed for this study by the research assistants. The PI will perform periodic review of the data entry process to ensure accuracy of recording. When study results are published or presented, only aggregate reports of the results will be used and participants' identity will not be revealed. A file of name, contact address, telephone number, and other research identification numbers will be stored separately on paper and on computer, for purposes of audit by the MUSC IRB, if necessary.

In the event of negative interactions between the lay patient navigator/care coordinator and patients, the following steps will be taken:

1. The PI will communicate with patients and the lay patient navigator on a weekly basis to assess calling patterns, content of calls, any other interactions between the lay patient navigator and patient(s), and any concerns either may have.
2. Patients and the lay patient navigator will be encouraged to contact the PI at any time if they run into a difficult situation with a patient. If during such communication, patient or the lay patient navigator reports that they believe that their patient/lay patient navigator may be depressed, homeless/displaced, suicidal, has broken confidentiality, is repeatedly asking for medical advice, prying too much into their personal life, or that they are simply not connecting, the PI will meet with each party individually to discuss, troubleshoot, and develop solutions or direct to services, when applicable.
3. If the patient/lay patient navigator does not resolve the issue successfully on their own (with the exception of issues of suicidality, depression, and homelessness, which they are instructed to turn over to the PI to handle/address), the PI will meet with the pair together to discuss, troubleshoot, and develop solutions.

4. If the patient and lay patient navigator agree to continue, but report that issues can/have not been resolved, the PI will remove that patient from the study.

5. If complaints persist about a specific patient or the lay patient navigator that contradict study procedures (e.g., breaking confidentiality, not adhering to intervention format), that participant could be asked to leave the study. If multiple patients express discontent with the lay patient navigator, the study will be terminated.

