Process Measures and Secondary Outcomes. To assess for differences in outcome expectancy, a modified treatment credibility scale developed by Borkovec and Nau (1972) will be used. Satisfaction with Care will be measured with a previously validated general scale to measure satisfaction/dissatisfaction with health care. Other covariates will be measured by previously validated items from the 2002 National Health Interview Survey [NCHS 2004] to capture age, marital status, education, household income, and health insurance; the Chew Health Literacy Screening Survey[195] to detect potential health literacy problems; the Arthritis Self-Efficacy Scale pain and other symptoms sub-scale, arthritis.[196,197] which measures confidence in one's ability to manage the pain, fatigue, frustration, and other aspects of disease; the PHQ-9, which scores each of the 9 DSM-IV criteria for depression;[198,199] and the 7-item General Anxiety Disorder scale (GAD-7).[200]

Analysis Plan

Aim 1 - Feasibility analyses: Important measures of feasibility will include recruitment, compliance, non-response proportions and participant satisfaction. We will use 95% confidence intervals (CI) for proportions to estimate the proportion of participants who agree to participate out of the number who are initially approached, the proportion who are compliant with the treatment protocol, and the proportion who exit the study prematurely (drop out). In addition, frequency distributions describing the participants' reasons for noncompliance and discontinuation of study participation will be developed. We will also evaluate patient satisfaction with the lay patient navigator/care coordinator services using a likert-type satisfaction scale. For the continuous feasibility measures (e.g. treatment credibility, treatment adherence, phone sessions and attrition), frequency distributions and the median and mean responses (with 95% CIs) will be obtained.

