- Describe any data that will be recorded on the human subjects involved in the project.
- Describe the linkages to subjects, and indicate who will have access to subject identities.
- Provide information about how the specimens, records, or data are collected and whether material or data will be collected specifically for your proposed research project.

1. Research Material & Data: Sources of research material include medical records and research questionnaires.
2. Linkages to Subjects: Subjects will provide identifying information in addition to research data. Paper documents pertaining to this study will be stored in locked file cabinets in both the clinical center and the data

management center, and data will be entered into secure, password-protected web databases developed for this study. A database of name, contact address, telephone number, and other research identification numbers will be stored separate from the study database, for purposes of audit by the MUSC IRB, if necessary. Access to study data will be limited to research personnel.

3. Collection of Data and Specimens:

Personnel: A part-time lay patient navigator will be responsible for consent, enrollment and data collection, a part time health economist will be responsible for accessing and analyzing resource use and cost data, and a part-time data coordinator (DC) will be responsible for data management and analyses for patient reported outcomes. **Data Collection Schedule:** At the baseline visit, the lay patient navigator will give detailed explanation of the study, the reimbursement schedule, and obtain consent. Participants will complete a questionnaire that captures demographics, health literacy, coping, disease activity, disease self-management, anxiety, depression, and quality of life. The lay patient navigator will review study goals, establish the schedule of study sessions, obtain contact information (primary and alternate telephone numbers), and receive study materials. After the baseline assessment, follow-up assessments will be conducted at 6 weeks and 12 weeks. As much as possible, research visits will be scheduled on the same day as their clinic visit.

c. Potential Risks

- Describe the potential risks to subjects (physical, psychological, social, legal, or other), and assess their likelihood and seriousness to the subjects.

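### Same-visit clinician assessment depends only on a positive PHQ-9 depression screen, so a suicidality answer with a negative screen requires no assessment before the participant leaves

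*Protocol*

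**What the plan says.** Section E.2.b, under the additional protections, explains that because a depression questionnaire is given, steps will be taken for participants' safety. The PI trains research personnel to "identify patients who meet criteria for depression on the PHQ-9". The action follows from that result: "Participants who screen positive for depression will be assessed by a clinician before leaving their study visit to ensure their well-being". The advice to see the primary care physician and the suicide hotline, the latter only where deemed appropriate, are for the same screened-positive group. No cut-off or scoring rule is given, and no single item is named.

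Section D (Process Measures and Secondary Outcomes) describes the instrument as "the PHQ-9, which scores each of the 9 DSM-IV criteria for depression".

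Suicidality appears elsewhere only in the later list in E.2.b that opens "In the event of negative interactions between the lay patient navigator/care coordinator and patients, the following steps will be taken". There the navigator and patient are expected to settle problems themselves, "with the exception of issues of suicidality, depression, and homelessness, which they are instructed to turn over to the PI to handle/address".

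On who collects the data and when, section E.1.b says "A part-time lay patient navigator will be responsible for consent, enrollment and data collection", that after baseline "follow-up assessments will be conducted at 6 weeks and 12 weeks", and that "As much as possible, research visits will be scheduled on the same day as their clinic visit".

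**The concern.** The step exists to protect people who are asked about depression, and the hotline shows that suicide risk was in mind. Yet what sets the step in motion is the depression result, not the suicidality answer. These are different things: one endorsed criterion out of nine need not make the screen positive. Staff who follow the rule exactly could record a suicidality answer, find the screen negative, and let the participant go home with nothing further required.

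No estimate or test is affected. What is at stake is participant safety, where few cases are expected but the harm could be grave and irreversible. Baseline is less exposed, because it takes place at the recruitment visit of admitted patients who are already under hospital care. The follow-up visits are where the gap matters, and it applies to both arms.

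**Working it through.** The protocol gives no figure to reproduce. The check has three parts.

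**1. Every route that could lead to action on a suicidality answer**

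| Protocol text | What sets it off | Clinician required? | Before leaving the visit? |
|---|---|---|---|
| E.2.b, Psychological Distress | Positive depression screen | Yes | Yes |
| E.2.b, general clause on guidance from the PI | Need for intervention after a study-related event | No, guidance by the PI | No, only described as timely |
| E.2.b, steps for negative interactions | Report or belief that someone may be suicidal | No, goes to the PI | No timing set |
| E.1.b, visits aligned with clinic days | Scheduling | Not required | Only as far as possible |
| E.5, monitoring plan | Adverse events and reports | No visit-level rule | No |

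Only the first row requires a clinician before departure, and its trigger is the depression result.

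**2. Can a participant endorse suicidality and still screen negative?**

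Assumptions, since the protocol does not describe the items: one of the nine asks about suicidality, and each is scored 0 to 3. As no cut-off is stated, totals of 5, 10 and 15 and a count of at least 5 of 9 symptoms are tried. In the two illustrative records below, the last item is suicidality.

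- Record A = [0,0,0,0,0,0,0,0,3]. Total 3, negative at 5, 10 and 15. It has 1 of 9 symptoms whether an item counts from 1 or from 2.
- Record B = [1,1,0,0,0,0,0,0,2]. Total 4, negative at 5, 10 and 15. It has 3 of 9 symptoms if an item counts from 1, and 1 of 9 if from 2.

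With the suicidality item at its maximum of 3, the further points a participant can carry and stay negative are cut-off − 1 − 3:

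- cut-off 5: 5 − 1 − 3 = 1
- cut-off 10: 10 − 1 − 3 = 6
- cut-off 15: 15 − 1 − 3 = 11

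On the symptom count, suicidality plus three other symptoms is 4, which is below 5 and so negative. The gap exists under every rule tried.

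**3. Scale**

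Inputs: 40 patients (section D) and two follow-up visits (section E.1.b), assuming the PHQ-9 is given at both and nobody drops out. Screens = 40 × 2 = 80. Let p be the share of screens with suicidality endorsed and a negative screen. The protocol gives no value, so 1%, 3% and 5% are assumed.

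- Expected screens = 80 × p
- Chance of at least one, screens independent = 1 − (1 − p)^80
- Chance of at least one, a patient's two screens fully dependent = 1 − (1 − p)^40

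| p | Expected screens | At least one, independent | At least one, fully dependent |
|---|---|---|---|
| 0.01 | 0.8 | 0.553 | 0.331 |
| 0.03 | 2.4 | 0.913 | 0.704 |
| 0.05 | 4.0 | 0.983 | 0.871 |

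**The case against.** The strongest reply is that the protocol does not define a positive screen. It leaves that to the PI's training, which could include a rule for single items, so the text may be unspecified rather than too narrow. This is fair as far as it goes. But both the training instruction and the action are worded in terms of depression, and the ordinary reading is the result of the whole questionnaire. A safeguard that depends on an unstated training rule is not one the protocol requires.

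A second reply is that detection is likely in practice. Section D makes face-to-face interview the primary method of data collection, so an answer would probably be heard. The interviewer is the navigator, who hands suicidality to the PI and may contact the PI at any time. The general clause in E.2.b also promises timely guidance from the PI. These points stand and make the gap smaller in practice. None of them requires a clinician or sets action before the participant leaves, and the hand-over instruction is written for difficult relations between navigator and patient, not for questionnaire answers.

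A third reply is that the item content and scoring come from outside the protocol and that the rates are invented. Both are assumptions here. The chances of at least one case only restate the assumed rates and should carry no weight of their own. The main point does not depend on them: it needs only that suicidality is one of nine separately scored criteria and that one criterion alone need not make the screen positive.

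**Conclusion.** The concern holds. The one rule that requires a clinician before the participant leaves is triggered by a positive depression screen, and no rule acts on a suicidality answer by itself. This is a safety trigger set too narrowly for its stated purpose; it does not contradict other parts of the protocol. Such a case may well be caught by the interviewer or the PI, but nothing written requires it at that visit.

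The exposure is at most 80 follow-up screens across both arms. Under the assumed rates of 1% to 5%, between 0.8 and 4.0 of them would carry no required assessment. The conclusion rests on the usual content of the PHQ-9, which the protocol names but does not describe. The change should be made because it is cheap and concerns safety. Confidence is medium, given the undefined screening rule and the partial cover from other routes.

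**What to change.** In section E.2.b, Psychological Distress, add a sentence to this effect: in both arms, the PHQ-9 suicidality item is read before the participant leaves each study visit, and any endorsement, whatever the overall result, leads to the same clinician assessment already provided for positive screens. Add the point to the PI's PHQ-9 training of research personnel. What is done clinically remains the decision of the assessing clinician.

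The cost is one sentence and one training point. The questionnaire and the clinician assessment are already in place. The downside is a few more assessments, about 1 to 4 over the follow-up visits under the assumed rates.

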Overview of Study Design. The Care-coordination Approach to Learning Lupus Self-Management (CALLS) study is a double arm, pre-post pilot designed to examine whether modeling and reinforcement from a lay patient navigator/care coordinator improves disease self-management, indicators of disease activity, health related quality of life (HRQOL), and 30-day readmission in SLE inpatient admissions. We will recruit 40 patients (20 questionnaires and phone sessions and 20 questionnaires only) with active SLE upon hospital admittance at the Medical University of South Carolina (MUSC). The lay patient navigator/care coordinator will be trained to deliver intervention content by twelve weekly telephone sessions carried out across the course of the study. All participants will be assessed using validated measures of patient reported outcomes at baseline, mid-intervention (6 weeks post-enrollment), and immediately following the intervention (12 weeks post-enrollment). Outcomes for patients who agree to phone sessions will be compared with the outcomes of patients who opt to participate in questionnaires only. The study will last 12 months with recruitment and enrollment over 6 months, 3 months for intervention delivery and 3 months for data analysis.

Study Population. The total number of individual patients with systemic lupus erythematosus (SLE) currently being followed by clinicians at MUSC is 1,159 in the past six months that had this encounter diagnosis and 1,526 with this diagnosis in the chart history or problem list or encounter diagnosis, of which approximately 60% are African American and 90% are female. This will allow for the assessment of impact and cost savings/effectiveness according to underrepresented racial and gender categories. The target population for this study will be SLE inpatient admissions. There are approximately 35 SLE and Scleroderma hospital admissions each month, so it is expected that over a 3-month recruitment period, we will be able to recruit 40 participants (20 questionnaires and phone sessions and 20 questionnaires only).

Recruitment of Lay Patient Navigator/Care Coordinator

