Admitted SLE patients will be referred by their physician for participation in the study, who will provide a letter that will explain the study and provide participants a number to call if they have questions or concerns prior to agreeing to participate. Participants who indicate interest in the study will be immediately screened for eligibility, and if eligibility criteria are met, informed consent will be obtained. Once a patient has been consented, they will be randomized to membership in one of the two study arms. assigned to the intervention (complete questionnaires and phone sessions) or control (complete questionnaires only) arm, and the rest of the recruitment visit will include baseline self-report assessments and scheduling of phone sessions (if applicable). Preliminary data from our group suggests that those participants with the worse outcomes at baseline experienced the largest gains post-intervention, so the proposed intervention focuses on patients with high needs (as indicated by hospital admission) to reach those with the greatest potential for benefit from supportive services. This approach could ultimately incorporate the lupus nephritis risk prediction model/tool being developed by [name] to prevent renal failure and admissions due to renal flares.

Inclusion criteria for SLE patients include: 1) Hospital admission for SLE-related issue; 2) clinical diagnosis of systemic lupus erythematosus (SLE) from a physician; 3) 18 years of age or older; 4) able to provide informed consent and take part in ongoing assessment/evaluation activities (self-reported questionnaires); 5) able to commit to duration of study (3 months); 6) able to communicate in English; and 7) have an active phone line (landline or cell phone) for the duration of the study, if agreeing to phone sessions with the lay patient navigator/care coordinator. Exclusion criteria include: 1) cognitive impairment; 2) acute decompensation of chronic conditions precluding participation; 3) conditions that preclude participation in assessments (e.g. blindness or deafness); and 4) terminal illness or life expectancy less than 6 months as evaluated by physician.

Lay Patient Navigator/Care Coordinator Service Elements.

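### Removing a patient from the study, rather than from the phone sessions, when the navigator relationship fails loses questionnaire outcomes almost entirely from the intervention arm

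*Protocol*

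**What the plan says.** **The removal rule.** Section E.2.b (Protection against Risk) ends with numbered steps for negative interactions between navigator and patient. Item 4 covers a pair who are willing to continue but "report that issues can/have not been resolved, the PI will remove that patient from the study". It is mandatory, and it refers to the study, not to the sessions. Item 5 deals with persistent complaints that contradict study procedures, one example being failure to keep to the intervention format. There, "that participant could be asked to leave the study". Item 5 also says that the study will be terminated if several patients are discontented with the navigator.

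**Allocation.** Section D (Recruitment of SLE patients) and section E.2.a both say: "Once a patient has been consented, they will be randomized to membership in one of the two study arms". The arms are then described as "assigned to the intervention (complete questionnaires and phone sessions) or control (complete questionnaires only) arm". The Overview of Study Design reads differently: "Outcomes for patients who agree to phone sessions will be compared with the outcomes of patients who opt to participate in questionnaires only".

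**Who meets the patients.** Section E.1.b states: "A part-time lay patient navigator will be responsible for consent, enrollment and data collection". This is not limited to one arm.

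**Analysis.** Aim 1 estimates compliance and "the proportion who exit the study prematurely (drop out"), each with a 95% confidence interval, and tabulates reasons for noncompliance and discontinuation. Aim 2 fits a linear mixed model. The Sample Size Justification gives its terms as treatment, time, their interaction and a random subject effect. Readmission, medication refill and cost data come from medical records and the data warehouse.

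**The concern.** Ending the intervention and ending follow-up are different events, and item 4 merges them. A patient who has been randomized, and who may want to continue, leaves the study because the intervention relationship did not work. Control patients have no sessions and no intervention format to breach, so a comparable exit is hardly open to them.

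Nowhere does the protocol say that removed patients go on to complete the week 6 and week 12 assessments. If they do not, the questionnaire outcomes after removal are never collected, and no later analysis plan can recover them.

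The pilot exists to measure feasibility and to supply effect sizes for a larger trial. Differential loss tied to how the intervention was received affects both. In Aim 1 it also mixes the investigator's decision to remove a patient with the patient's own decision to drop out.

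**Working it through.** **1. Is the exclusion after randomization, and on which arm does it fall?** Sections D and E.2.a place randomization directly after consent. The removal steps operate later, once there have been interactions to monitor. They speak of call patterns, call content and meetings with the pair, which describes the intervention arm. Section E.1.b lets the navigator meet control patients for consent and data collection, and item 1 of the steps also covers other interactions. A control patient could therefore in principle be caught, so the supportable wording is *almost entirely* the intervention arm. If the self-selected groups of the Overview are meant instead, the loss still falls on the phone-session group, but it is no longer a departure from a randomized comparison. These passages must be reconciled.

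**2. What is lost?**
- Lost after removal: LUP-QOL, PAM, SLAQ and satisfaction, all obtained from the patient.
- Not necessarily lost: readmission, refill and cost data, which come from records.
- Kept: data collected before removal; nothing says they are deleted.

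**3. Can the mixed model make up for it?** It uses all observed visits and is valid if missingness depends only on observed data. Its terms contain nothing about rapport with the navigator. A patient removed before week 6 contributes baseline only. The assumption is hard to defend when the cause of missingness is failure of the intervention relationship.

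**4. The plan's own precision figure.** With 20 per arm and the SD of change as the unit:

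t(0.975, 38) × √(2/20) = 0.640, which reproduces the stated 0.64.

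With k intervention patients lost, the half-width is t(0.975, 38 − k) × √(1/(20 − k) + 1/20):
- k = 1: 0.649
- k = 2: 0.659

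Precision hardly changes. The issue is a possible shift of the estimate.

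**5. Size of the shift.** The protocol gives neither the number removed (k) nor how their change would differ from the rest (gap g, in SDs of change). Both are assumptions. Let the retained patients have mean change m:

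mean of all 20 = [(20 − k)m + k(m − g)]/20 = m − kg/20

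The retained patients show m, so the arm mean, and the between-group difference if no controls are lost, shifts by kg/20.

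| k | g = 0.5 | g = 1 | bound: the k worst of 20 removed (simulated, normal) |
|---|---|---|---|
| 1 | 0.025 | 0.05 | 0.10 |
| 2 | 0.05 | 0.10 | 0.18 |

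Against 0.64, a shift of 0.05 is about 8% of the half-width (0.05/0.64) and 0.10 about 16% (0.10/0.64). These are raw means. The mixed model can use baseline and any week 6 data, so its shift may differ.

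**6. Aim 1 compliance.** The protocol does not say whether removed patients stay in the denominator. As an illustration, if 14 of 20 comply (70%) and two removed non-compliers leave the denominator, the figure reads 14/18 = 78%.

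**The case against.** The other side has several good points.

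- **Few removals are likely.** Item 5 terminates the study if multiple patients are discontented, and an earlier item in E.2.b terminates it if the navigator feels uncomfortable or overwhelmed. Several removals for discontent would probably trigger one of these. That stands: one removal is the natural case and two is possible, for example where the complaint concerns a patient's conduct.
- **Removals stay visible.** Aim 1 counts premature exits and tabulates reasons, and the investigator's weekly contacts track satisfaction. That stands for Aim 1 reporting. It does not supply the missing Aim 2 questionnaires.
- **Item 5 is weaker than item 4.** It is discretionary, and the participant it refers to could be the patient or the navigator. That also stands, so item 4 carries the point.

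A reader might also infer more than the text supports:

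- *That removal can happen only in the intervention arm.* The navigator's consent and data-collection role rules out so absolute a statement.
- *That the worst experiences drop out and the result is biased towards the navigator.* The triggers include repeated requests for medical advice, a breach of confidentiality or simply not getting on. Nothing in the protocol links these to poorer change in LUP-QOL, PAM or SLAQ.
- *That readmissions go missing.* They come from records, and nothing says extraction stops at removal.
- *That satisfaction would be inflated by a calculable percentage.* Satisfaction is a Likert-type scale, with no proportion satisfied defined and no denominator fixed.

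**Conclusion.** The point holds in a limited form. Item 4 turns a failed navigator relationship into the end of study participation, after allocation and almost entirely in one arm, and no provision keeps the questionnaires going. Following the plan as written loses outcome data differentially, and this cannot be put right at the analysis stage.

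Bias in favour of the navigator is plausible but not shown. Under assumed gaps of 0.5 to 1 SD the shift is 0.025 to 0.05 SD for one removal and 0.05 to 0.10 SD for two, small beside the planned half-width of 0.64 SD. Describing the loss as post-randomization relies on sections D and E.2.a rather than the Overview of Study Design. The case for changing the rule is that the loss is avoidable at very little cost, not that the expected bias is large.

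**What to change.** Leave the sponsor's rule for ending navigator sessions as it is. Reword items 4 and 5 of the negative-interaction steps so that ending sessions does not end study follow-up. Unless they withdraw consent, such patients should:

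- still complete the week 6 and week 12 questionnaires, administered by existing research personnel other than the navigator;
- remain in the extraction of readmission, refill and cost records;
- be analysed in their randomized arm;
- stay in the Aim 1 compliance denominator as non-compliant.

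Report investigator-ended sessions separately from drop-out. State in item 5 whether the participant meant is the patient or the navigator. Reconcile the Overview of Study Design with the randomization text in sections D and E.2.a.

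The cost is protocol and consent wording and a few additional follow-up questionnaires, for which someone other than the navigator must be available. With these patients retained, the comparison stays at 20 against 20 and, if they complete the questionnaires, this rule adds no bias.
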